1.4.3. Extranodal Index Lesions

An extranodal mass may be selected as an index lesion if it is both abnormal and measurable at baseline. An extranodal mass of any size is considered abnormal. It is considered measurable at baseline if it has 2 perpendicular diameters that can be accurately measured in cross section with the LD being ≥ 1.0 cm and the LPD also being ≥ 1.0 cm.

At follow-up timepoints, the PPD of each single extranodal index lesion and the SPD of all extranodal index lesions will be considered. Because extranodal index lesions that have one or both diameters < 0.5 cm and > 0 cm cannot be reliably measured, a default value of 0.5 cm will be assigned for each diameter that meets these criteria and the resulting PPD will be used in SPD calculations. If an extranodal lesion is no longer clearly visible, it will be considered resolved and its PPD will be defined as 0 cm².

If an extranodal lesion that had resolved (i.e., had a PPD of 0 cm²) subsequently reappears, the subject will be considered to have PD. A new extranodal lesion of any size that appears at a site that was not previously involved with lymphoma and is discernible to the radiologist by CT scan will be considered PD.

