1.5.4. Progressive Disease

The occurrence of any of the following events indicates progressive disease (PD):

- Evidence of any new disease that was not present at baseline:
 - A new node that measures > 1.5 cm in any diameter
 - A new node that measures > 1.0 cm to ≤ 1.5 cm in the LD and > 1.0 cm in the LPD

- Reappearance of an extranodal lesion that had resolved (i.e., had previously been assigned a PPD of 0 cm²)
- A new extranodal lesion of any size
- New non-index disease (e.g., effusions, ascites, or other organ abnormalities) of any size unequivocally attributable to lymphoma (usually requires PET, biopsy, cytology, or other non-radiologic confirmation to confirm disease attributable to lymphoma). Note: Isolated new effusions, ascites, or bone lesions are not sufficient evidence alone of PD unless histologically confirmed. In patients with no prior history of pulmonary lymphoma, new lung nodules identified by CT are usually benign. Thus, a declaration of PD should not be made if this is the only manifestation of an apparently new lesion.
- New FDG-avid foci consistent with lymphoma rather than another etiology (e.g., infection, inflammation). If there is uncertainty regarding the etiology of new lesions, biopsy or interval scan may be considered.
- New or recurrent bone marrow involvement with lymphoma by PET-CT or by bone marrow biopsy if prior PET-CT or bone marrow biopsy performed as part of the study was negative for lymphoma.
- Evidence of worsening of nodal or extranodal index lesions:
 - Increase from the nadir by $\geq 50\%$ in the SPD of index lesions
 - Evidence of worsening of individual index lymph nodes or nodal masses:
 - Increase from the nadir by $\geq 50\%$ in the PPD for any individual node if the node now has an LD of > 1.5 cm and there is an absolute change from the nadir of ≥ 0.5 cm in the LD or LPD and to an absolute dimension of ≥ 2.0 cm.
 - ➤ Increase from the nadir by $\geq 50\%$ in the LD for any individual node if the node now has an LD of > 1.5 cm and there is an absolute change from the nadir of ≥ 0.5 cm in the LD
 - ➤ Increase from the nadir by $\ge 50\%$ in the LPD for any individual node if the node now has an LPD of > 1.5 cm and there is an absolute change from the nadir of > 0.5 cm in the LPD
 - ➤ If a lesion had been classified as a small lymph node, there is an additional requirement that the lesion has an LD of > 1.0 cm and an LPD of > 1.0 cm
 - Unequivocal increase in the size of non-index disease

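### For NHL, Appendix 2 section 1.4.3 calls an isolated new lung nodule or unbiopsied bone lesion progression, while the Note in section 1.5.4 says it is not

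*Combined protocol and SAP*

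**What the plan says.** Appendix 2, Section 1 sets the NHL response criteria. Two of its sections deal with new extranodal lesions.

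- **1.4.3 (Extranodal Index Lesions).** The last sentence applies to "A new extranodal lesion of any size that appears at a site that was not previously involved with lymphoma". If the radiologist can see such a lesion on CT, the stated consequence is PD. The sentence names no organ exception and does not refer to 1.5.4.
- **1.5.4 (Progressive Disease).** Any one listed event is enough for PD. The list includes "A new extranodal lesion of any size", with no condition on site. A Note under the neighbouring bullet on new non-index disease makes two exceptions. For effusions, ascites and bone: "Isolated new effusions, ascites, or bone lesions are not sufficient evidence alone of PD unless histologically confirmed". For lung: "In patients with no prior history of pulmonary lymphoma, new lung nodules identified by CT are usually benign", followed by the instruction that "a declaration of PD should not be made if this is the only manifestation of an apparently new lesion".

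A closing note in 1.5.4 lets the investigator keep a subject under observation when progression is uncertain, with evaluations for example every 3 to 6 weeks. If definitive progression is later established, it is dated to when it was first objectively documented. Section 6.12 has the same dating rule.

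**The concern.** Response is assessed by the investigator (Section 5.5) in an open-label study with about 15 expansion sites planned (Synopsis). Sections 8.4 and 11 send the reader to Appendix 2 for the criteria and do not rank its sections. The text available describes no central review that would impose one reading, so two investigators following the protocol could record opposite outcomes for the same scan.

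The PD call feeds several results. CR, PR and SD each require the absence of new disease (Appendix 2, 1.5.1 to 1.5.3). Best overall response counts only what is recorded before PD (1.5). Duration of response and PFS both use the progression date (Section 14.9). PD is also a listed reason for withdrawal from treatment (Section 6.12), which is one more reason to reconcile the two sections.

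**Working it through.** The plan gives no figure to reproduce. The check applies both sections to the same scan.

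| Only new finding on the scan | Under 1.4.3 | Under 1.5.4 | Result |
|---|---|---|---|
| CT lung nodule, no earlier pulmonary lymphoma | PD: uninvolved site, any size, seen on CT | Note: PD should not be declared | Direct conflict |
| Bone lesion without histology, bone not involved before | PD on a literal reading | Note: not sufficient alone | Conflict |
| Extranodal lesion at an already involved site | Does not meet the stated condition | PD under the extranodal bullet | Scope mismatch |
| Lesion outside lung and bone, at an uninvolved site | PD | PD | Agreement |

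The first row is enough to establish the point. Section 1.5.4 is also strained internally: its extranodal bullet taken alone would call the lung nodule PD, and the Note that says otherwise is attached to a different bullet.

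**Time at stake.** If the call differs, PD is recorded at that scan or not before a later qualifying event. Scheduled scan spacing indicates the gap.

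- Monotherapy and rituximab cohorts: scans at Cycles 3, 5 and 7 with 28-day cycles, so 2 × 4 = 8 weeks early on, then 12 weeks or 3 months (Tables 8 to 10).
- Atezolizumab cohorts: Table 11 equates 4 cycles with 12 weeks, so a cycle is 3 weeks and early scans are 2 × 3 = 6 weeks apart, then 12 weeks.
- Monotherapy subjects still in response after 1 year: up to 6 months (Tables 8 and 9).

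Observation under the closing note of 1.5.4 can shorten these gaps, and its dating rule can remove the shift for a lesion later shown to be progression.

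**Response rate.** A lesion that appears after a response has been recorded leaves best overall response unchanged. A lesion at or before the first response scan can change it. In a six-subject cohort one subject is 1/6 = 16.7 percentage points.

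The follicular lymphoma cohorts of up to about 20 (Section 14.1.2) illustrate the effect at the final boundary. For r responders of n, the exact one-sided 95% lower bound is the 5th percentile of a Beta(r, n − r + 1) distribution.

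| Cohort | At the boundary | One responder fewer | Rate to exclude |
|---|---|---|---|
| Monotherapy | 8/20 = 40%, bound 21.7% | 7/20 = 35%, bound 17.7% | 20% |
| With rituximab | 12/20 = 60%, bound 39.4% | 11/20 = 55%, bound 34.7% | 39% |

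In both cohorts, losing one responder at the boundary takes the lower bound below the rate to be excluded.

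**The case against.** The strongest defence is that 1.5.4 is the section that defines PD, that its Note is the more specific text, and that a sensible reader would let it govern. That reading is reasonable, but the appendix does not state it, and 1.4.3 is worded as a rule in its own right.

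Parts of the defence stand and limit the point.

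- A reader might infer that 1.4.3 confines PD to previously uninvolved sites. It does not: it gives a sufficient condition and is silent on involved sites, which 1.5.4 covers. That row is a mismatch in scope, not an express contradiction. For new liver nodules, 1.4.5 also bears on the call, because it ties hepatic progression to enlargement together with a nodule.
- A reader might infer that, because the lung sentence lacks the histology release given to effusions, ascites and bone, a subject with proven lung lymphoma would stay in response indefinitely. The documents do not support that. Section 1.5.4 has other routes to PD: new non-index disease clearly attributable to lymphoma, new FDG-avid foci, and unequivocal growth of non-index disease. The uncertainty and dating rule also applies. These routes may capture some true lung progression, although PET is not a required assessment (Appendix 2, 1.2). What remains is an unexplained difference between adjacent sentences.
- The bone case is slightly less clean than the lung case. It depends on counting a bone lesion as an extranodal lesion, and 1.4.4 lists the two separately.
- The uncertainty rule covers doubt about whether disease has truly progressed. It does not say which of two written definitions applies.

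**Conclusion.** The inconsistency is real and should be corrected. An isolated new CT lung nodule in a subject without earlier pulmonary lymphoma is PD under 1.4.3 and not PD under the Note in 1.5.4. An isolated new bone lesion without histology conflicts in the same way if it is counted as extranodal. The site condition in 1.4.3 and the missing histology release for lung are secondary ambiguities.

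For an affected subject, the progression date, duration of response and PFS can change. The response rate moves only when the lesion precedes or coincides with the first response scan, by 17 percentage points per subject in a six-subject cohort. It would be wrong to infer that every such lesion alters the response rate. The frequency of such scans is not given, so no expected bias can be stated.

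The conclusion assumes that no precedence rule exists elsewhere. Only the first of two parts of the combined document was available, so this could not be checked in the remainder.

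**What to change.** Make 1.5.4 the single definition of PD for NHL and have 1.4.3 defer to it.

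1. Replace the last sentence of 1.4.3 with, for example: *New extranodal lesions are assessed for PD as defined in 1.5.4, including its Note.* This also removes the site condition that 1.5.4 lacks.
2. Make clear in 1.5.4 that the Note, with both its lung and its bone exceptions, qualifies the bullet on new extranodal lesions.
3. State in the Note whether the lung exception is lifted by histological confirmation, as it is for effusions, ascites and bone lesions. Any later-established progression keeps the dating rule already in the closing note of 1.5.4.

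The bone exception must be carried over explicitly. A rule exempting only lung nodules would make an unbiopsied bone lesion PD, against the same Note.

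The cost is about two sentences in Appendix 2, with no added scan, biopsy or visit. If the protocol is not amended again, the same convention can be written into the analysis plan before the database lock described in Section 6.1.3.

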1.4.4. Non-Index Lesions

Any other measurable and abnormal nodal or extranodal lesions not selected for quantitation as index lesions may be considered non-index lesions. In addition, non-measurable evidence of lymphoma such as abnormal, non-measurable nodal lesions, extranodal lesions with both diameters < 1.0 cm, bone lesions, leptomeningeal disease, ascites, pleural or pericardial effusions, lymphangitis of the skin or lung, abdominal masses that are not confirmed and followed by imaging techniques, cystic lesions, previously irradiated lesions, or lesions with artifacts may be considered as non-index disease.

If present at baseline, up to 6 non-index lesions should be recorded. Measurements are not required.

Non-index disease will be used as a general reference to further characterize regression or progression of lymphoma during assessments of the objective tumor response during treatment. These lesions should be followed as "present" or "absent".

Version 9, 18 Feb 2020

1.4.5. Spleen and Liver

Qualitative assessments of the sizes of the spleen and liver will be performed. In addition, the presence or absence of splenic nodules will be recorded.

At baseline and follow-up timepoints, the spleen and liver size will be reported as normal, enlarged not due to lymphoma (no nodules present), enlarged due to lymphoma (≥ 1 nodule present), unequivocal increase not due to lymphoma (no nodules present), or unequivocal progression (≥ 1 nodule present). For subjects with splenomegaly or hepatomegaly at baseline or at the nadirs for assessments of spleen and liver, evaluations will consider only changes relative to the enlargement of the organ (i.e., the portion of the LVD that is > 12 cm by imaging for the spleen and > 18 cm in LVD for the liver) at baseline or nadir, not changes relative to the total splenic LVD.

By imaging, the spleen will be considered enlarged if it is > 12 cm in LVD (Bezerra 2005, Asghar 2011), with the LVD being obtained by multiplying the number of sections on which the spleen is visualized by the thickness of the sections (e.g., if the spleen is seen in 14 contiguous cross-sectional images with 0.5-cm thickness, the LVD is recorded as 7 cm). An increase in splenic enlargement by $\geq 50\%$ (minimum increase of 2 cm) from nadir and the presence of ≥ 1 splenic nodule is required for declaration of splenic progression. Subjects with a normal spleen LVD (i.e., a LVD of ≤ 0 cm by physical examination or ≤ 12 cm by imaging) at nadir will only be considered to have progressed if the spleen attains a LVD of ≥ 14 cm by imaging and there is ≥ 1 splenic nodule.

By imaging, the liver will be considered enlarged if it is > 18 cm in LVD (Erturk 2006). An increase in liver enlargement by \geq 50% (minimum increase of 2 cm) from nadir and the presence of \geq 1 hepatic nodule is required for declaration of hepatic progression. Subjects with a normal liver LVD (i.e., a LVD of \leq 18 cm by imaging) at nadir will only be considered to have progressed if the liver attains a LVD of \geq 20 cm by imaging and there is \geq 1 hepatic nodule.

1.4.6. Bone Marrow

Bone marrow assessments will be based on morphologic evaluation of bone marrow biopsies. Immunohistochemistry may be used to assess response if the sample is indeterminate by morphology.

In a subject who has a baseline bone marrow biopsy showing bone marrow lymphoma or does not have a baseline bone marrow examination, declaration of an on-study CR requires bone marrow biopsy documentation of the absence of bone marrow lymphoma. In a subject who has a baseline bone marrow biopsy showing no evidence of lymphoma, declaration of an on-study CR does not require bone marrow examination as long as other criteria for CR are met. Of note, in subjects with an FDG-PET avid lymphoma, declaration of an on-study CR can be based on FDG-PET documentation of the absence of bone marrow involvement, even if a bone marrow biopsy is not performed or not available.

1.4.7. Lymph Node Biopsy

Lymph node biopsy is not required in the determination of subject eligibility.

Version 9, 18 Feb 2020

During study participation, a subject with a more indolent type of disease (e.g., CLL/SLL, FL) who has a lymph node biopsy indicating transformation to an aggressive lymphoma will be considered to have PD even in the absence of other evidence of PD. If the subject has no earlier objective documentation of PD, the date of the lymph node biopsy will be considered the date of PD.

1.5. Definitions of Tumor Response and Progression

Responses will be categorized as complete response (CR), partial response (PR), stable disease (SD), or progressive disease (PD). In addition, a response category of nonevaluable (NE) is provided for situations in which there is inadequate information to otherwise categorize response status.

The best overall response will be determined. The best overall response is the best on-treatment response from baseline recorded from the start of treatment until PD/recurrence. The baseline measurement will be taken as a reference for determinations of response. The nadir measurement will be taken as a reference for PD; this measurement constitutes the smallest measurement recorded, including the baseline measurement if this is the smallest measurement. For FDG-avid tumors, metabolic criteria for response by PET-CT will take precedence over anatomic criteria for response by contrast CT when assessing CR.

1.5.1. Complete Response

To satisfy criteria for CR, all of the following conditions must be attained:

- No evidence of new disease
- Regression of all index nodal lesions to normal size (≤ 1.5 cm in the LD for nodes that were considered large at baseline and ≤ 1.0 cm in the LPD for nodes that were considered small at baseline) (see Section 1.4.2 for definitions of large and small nodes)
- Regression to normal of all nodal non-index disease
- Disappearance of all detectable extranodal index and non-index disease
- Normal spleen and liver size by imaging studies, no hepatic or splenic lymphoma nodules, and no new liver or spleen enlargement
- Morphologically negative bone marrow based on an adequate unilateral core biopsy (> 20 mm unilateral core); if the sample is indeterminate by morphology, it should be negative by immunohistochemistry
- If PET performed, no evidence of residual disease i.e., score of 1 (no uptake above background), 2 (uptake ≤ mediastinum), or 3 (uptake > mediastinum but ≤ liver) on the Deauville 5-point scale.
- Negative for bone marrow involvement by PET for a PET-avid tumor or by an adequate unilateral core biopsy (> 20 mm unilateral core); if the bone marrow biopsy is indeterminate by morphology, it should be negative by immunohistochemistry.

Version 9, 18 Feb 2020

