1.5.2. Partial Response

To satisfy criteria for PR, all of the following conditions must be attained:

- No evidence of new disease
- A \geq 50% decrease from baseline in the SPD of the index nodal and extranodal lesions
- No increase from the nadir in the size of non-index disease
- No increase from the nadir in the size of the liver or spleen and no new liver or spleen enlargement
- If PET performed:
 - Typically FDG-avid lymphoma: if no baseline PET scan or if the PET scan was positive before therapy, the on-treatment PET is positive in ≥ 1 previously involved site– i.e., score of 4 (uptake moderately > liver) or score of 5 (uptake markedly > liver) on the Deauville 5-point scale but with reduced uptake compared with baseline. If baseline PET was performed and was negative, there is no new PET evidence of disease.
 - Variably FDG-avid lymphoma/FDG-avidity unknown: if no pretreatment PET scan or if the pretreatment PET scan was negative for lymphoma, CT criteria should be used in assessing the tumor during treatment. If the PET scan was positive before therapy, the on-treatment PET is positive in ≥ 1 previously involved site.
- Persistence of bone marrow involvement in a subject who meets other criteria for CR based on the disappearance of all nodal and extranodal masses

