1.5.3. Stable Disease

To satisfy criteria for SD, all of the following conditions must be attained:

- No evidence of new disease
- Neither sufficient tumor shrinkage from baseline to qualify for PR nor sufficient evidence of tumor growth to qualify for PD
- If PET-CT performed, the results show a score of 4 (uptake moderately > liver) or score of 5 (uptake markedly > liver) on the Deauville 5-point scale with no significant change in uptake compared with baseline.

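### Appendix 2, 1.5.1 demands a negative marrow biopsy for every CR, against 1.4.6 and its own last bullet; applied literally, some PET-negative responders fit no response category

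*Combined protocol and SAP*

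**What the plan says.** References are to the lymphoma part of Appendix 2 unless a protocol section is named.

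- **CR (1.5.1).** The list opens "To satisfy criteria for CR, all of the following conditions must be attained". Two of its eight bullets concern the marrow. The sixth is "Morphologically negative bone marrow based on an adequate unilateral core biopsy"; it adds only that immunohistochemistry settles an indeterminate sample. The eighth is "Negative for bone marrow involvement by PET for a PET-avid tumor or by an adequate unilateral core biopsy".
- **Marrow rules (1.4.6).** If the baseline marrow was involved or not examined, "declaration of an on-study CR requires bone marrow biopsy documentation of the absence of bone marrow lymphoma". If the baseline biopsy was negative, "declaration of an on-study CR does not require bone marrow examination as long as other criteria for CR are met". In FDG-avid lymphoma, "declaration of an on-study CR can be based on FDG-PET documentation of the absence of bone marrow involvement", even without a biopsy.
- **PR (1.5.2).** This is also an all-of list. If PET is done in typically FDG-avid disease with a positive or absent baseline PET, PR requires that "the on-treatment PET is positive in ≥ 1 previously involved site". Variably avid disease with a positive baseline PET has the same requirement. The other branches do not ask for a positive PET. The last bullet of the list is persistent marrow involvement.
- **SD (1.5.3).** "If PET-CT performed, the results show a score of 4 (uptake moderately > liver) or score of 5" is one of the conditions.
- **NE (1.5.5).** Limited to missing or inadequate images.
- **Use of the categories.** Protocol section 14.9 counts best overall response of CR or PR as objective response. Section 14.1.2 sets the follicular lymphoma (FL) boundaries, ending at 8/20 for monotherapy and 12/20 with rituximab.

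**The concern.** Under an all-of heading, an unconditional biopsy bullet makes the PET option in the eighth bullet inoperative and overrides both waivers in 1.4.6. The negative-baseline waiver appears in neither bullet.

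Unbiopsied subjects are to be expected. Section 8.1.5 lets baseline marrow be omitted in NHL. Section 11 and the schedule footnotes call for repeat marrow only where the response criteria make it necessary, which leads back to the conflicting list.

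If a site applies the sixth bullet, there may be no lower category to fall to, because PR and SD carry PET conditions that a PET-negative subject cannot meet. Response is investigator-assessed (section 5.5), so sites may resolve the conflict differently. The subjects affected are among the deepest responders, and the FL decisions can turn on one response.

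**Working it through.** **Step 1: apply the lists.** Take a subject with complete CT regression, no new disease and no on-study biopsy. The PR bullet on persistent marrow involvement is set aside here; read literally it would block nearly every PR.

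| FDG avidity | Baseline PET | On-treatment PET | Sixth bullet literal | Sixth bullet subject to 1.4.6 and the eighth |
|---|---|---|---|---|
| Typical | positive or none | negative | no category | CR |
| Typical | negative | negative | PR | CR |
| Variable or unknown | positive | negative | no category | CR only if treated as PET-avid or baseline marrow biopsy negative |
| Variable or unknown | negative or none | negative | PR | PR, or CR if baseline marrow biopsy negative |
| Either | any | not done | PR | PR, or CR if baseline marrow biopsy negative |

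In the no-category rows:
- CR fails on the sixth bullet.
- PR fails because the on-treatment PET is negative.
- SD fails because it needs Deauville 4 or 5 (and the shrinkage is too great).
- No PD event has occurred.
- The images are adequate, so NE does not apply.

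**Step 2: reproduce the plan's boundaries.** The exact 1-sided 95% lower bound L solves P(X ≥ x | n, L) = 0.05.

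- 8/20 = 40%: L = 21.7%; P(X ≥ 8 | 20, 0.20) = 0.032. The plan claims at least 20%, and this agrees.
- 12/20 = 60%: L = 39.4%; P(X ≥ 12 | 20, 0.39) = 0.047. The plan claims at least 39%, and this agrees.

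**Step 3: remove one responder.**

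| Case | Monotherapy | With rituximab |
|---|---|---|
| At the boundary | 8/20, L = 21.7% | 12/20, L = 39.4% |
| One response lost, subject stays in the denominator | 7/20 = 35%, L = 17.7% | 11/20 = 55%, L = 34.7% |
| Subject also judged not evaluable | 7/19 = 36.8%, L = 18.8% | 11/19 = 57.9%, L = 36.8% |

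Every count in the last two rows misses its boundary (the listed values at N = 19 are 8/19 and 12/19).

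**Step 4: sensitivity.** Let m be the share of true responders left unclassified. The documents do not give m, so 0 to 30% is an assumption. The observable ORR is p(1 − m). The probability of meeting the boundary at N = 20, ignoring earlier looks, is:

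| m | P(≥ 8/20), p = 40% | P(≥ 12/20), p = 60% |
|---|---|---|
| 0 | 0.58 | 0.60 |
| 10% | 0.44 | 0.38 |
| 20% | 0.29 | 0.20 |
| 30% | 0.17 | 0.08 |

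**The case against.** The strongest reply is that the appendix, read as a whole, settles the matter. Section 1.4.6 is the marrow-specific provision and lets PET stand in for biopsy in FDG-avid lymphoma; the eighth CR bullet repeats that choice. An FL subject treated as FDG-avid, with Deauville 2 and a PET-clear marrow, is then CR without a biopsy. This is a reasonable reading and may well be the intended one. But no text gives 1.4.6 or the eighth bullet priority over the sixth. The precedence rule in 1.5 ranks PET-CT over contrast-CT criteria, and a biopsy is not a CT criterion.

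It can also be said that strict literalism proves too much, since the marrow-persistence bullet in 1.5.2 would then defeat almost every PR. That is true, and it is a reason to correct both lists.

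Several limits on frequency stand in full. PET is optional (1.2). PR demands a positive PET only in some branches. A PR recorded at an earlier scan is kept as best overall response (1.5). Response is a secondary endpoint, and a count exactly on the boundary is a knife-edge case.

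Four stronger inferences are tempting, and the documents do not support them:

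- *Section 1.4.6 waives biopsy generally.* It waives it for two groups and otherwise keeps it where the baseline marrow was involved or unexamined.
- *Every PET-negative, unbiopsied responder is unclassifiable.* Only two rows of the first table are, and only under the literal sixth bullet.
- *These subjects drop out of the ORR altogether.* Section 14.3.1 keeps NE subjects in the full-analysis denominator as failures. That rule describes insufficient assessments, so it does not strictly cover a fully imaged subject. Leaving the denominator is possible only for the evaluable count, if the subject is judged not evaluable and replaced (6.1.5, 6.13).
- *About two of eight FL responders are exposed, because 2 of 9 FL responses were CR (4.1.4.2).* Those nine pool three regimens, and the two were already recorded as CR.

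**Conclusion.** The contradiction is plain on the face of 1.5.1 and 1.4.6 and should be corrected. Its consequence is conditional: only if the sixth bullet is applied literally do the PET-negative, unbiopsied subjects in the two no-category rows meet none of CR, PR, SD, PD or NE. Such a subject, absent an earlier PR, is lost from the ORR numerator, or is counted at one site and not at another. Loss from the numerator biases the ORR downward.

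The number affected cannot be derived from the documents. What can be shown is the sensitivity: one lost responder at 8/20 or 12/20 misses the boundary. The probabilities for 10 to 30% loss rest on an assumed share and on the final look alone.

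The conclusion rests on the protocol body and Appendix 2. Section 14.2 leaves detailed methods to the SAP, whose response-derivation rules were not among the text examined. A rule there fixing which marrow provision governs would close the gap.

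**What to change.** 1. In 1.5.1, delete the sixth bullet or make it expressly subject to 1.4.6. Keep the eighth and add *or baseline marrow biopsy negative, per 1.4.6*.
2. In 1.5.2, state that a subject is PR who meets all the other PR conditions (nothing new, SPD down by at least 50% from baseline, no increase in non-index disease, liver or spleen) and has a negative on-treatment PET but misses a CR condition. The other conditions must stay in the sentence: without them, a PET-negative subject with a new lesion that 1.5.4 calls PD could be labelled PR.
3. In 1.5.2, make persistent marrow involvement an alternative route to PR rather than one of the all-of conditions. Together with item 2, this also settles the PET-negative subject whose biopsy still shows marrow lymphoma.

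The same rule should appear in the SAP's response derivation so that all sites' records are classified alike. The cost is wording in Appendix 2 and the SAP; no scan, biopsy or visit is added.
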